**History of protocol amendments approved by McGill University's Research Ethics Board**

(Refer to Appendix 1):

- Recruitment age increased from 18-26 years to 18-40 years (approved April 14, 2014).
- Maximum duration of relationship increased from 3 to 6 months (approved April 30, 2014).
- Compensation increased from CAD 350 to CAD 500 per couple (approved February 9, 2015). The above protocol changes were made to improve recruitment and/or simplify the logistics of the study.
- Gardasil 9 as intervention vaccine: The additional amendment relating to Gardasil 9 will enhance the health benefit of the study to participants while making this protocol truly cutting-edge with respect to the state of HPV science (approved July 08, 2015).
- Recruitment age increased from 18-40 years to 18-45 years (approved February 16, 2016).
- Discontinuing anal sampling: potential and current participants have confirmed our suspicions that troubling recruitment rates are due partially to the embarrassing and uncomfortable nature of this procedure (approved July 14, 2016).
- Adding a recruitment site in New York to increase the rate of accrual of participants (approved April 3, 2017).
- Compensation increase from CAD 500 to CAD 1000 per couple (approved May 8, 2017)
- Switch the placebo vaccine from Havrix to Avaxim (requested June 4, 2018, approved June 12, 2018).
- Second Oral Tube Collected: [name] transfers the sample to a freezer tube with tampon (she calls it "TE") - [name] removes the residues of the mouthwash and re-suspends it in the tampon. It's all kept in the freezer at [name] lab (information collected with [name] on February 11, 2022).
- Close study recruitment at 188 couples instead of the original 500 couples (requested on March 31, 2022, approved on May 26, 2022)
- Use of a different assay for serology testing (requested on September 8, 2022, approved on September 12, 2022) (Refer to Appendix 2)

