**2.10 Will health service research issues be addressed? Justify inclusion/exclusion of health economics and quality of life measures. If these measures are to be included full details should be given including power calculations.**

Health service research issues will not be directly addressed by the proposed study. However, should our trial demonstrate efficacy, its findings will be instrumental in orienting initial estimates of cost-effectiveness by our team or others. Our CIHR Team on HPV-associated diseases includes a health economist, [name], at Laval University. The results of this trial will assist in future analyses by [name]. Detailed information to inform future cost-utility analyses will be collected during the trial and will be made available to [name] (please see his letter).

**2.11 What is the proposed sample size and what is the justification for the assumptions underlying the power calculations? It is important to give the justification for the size of the difference that the trial is powered to detect. Does the sample size calculation take into account the anticipated rates of non-compliance and loss to follow-up given below?**

*Statistical power*

Empirically-based estimates of parameters for sample size calculation were obtained from our unit's molecular epidemiologic investigations of HPV infection of female university students, i.e., the McGill-Concordia cohort study and the "HPV Infection and Transmission among Couples through Heterosexual activity" (HITCH) cohort study, both funded by CIHR. The HITCH study is the same recruitment platform that will serve TRAP-HPV. Prevalence of the four Gardasil preventable HPV types (6,11,16, & 18) at enrolment was 23% and comparable between genders. The rate of acquisition of any of these types was 3.8 per 100 subject-months, which translates to approximately 40% cumulative incidence for these types in the unvaccinated HITCH population. The latter is the most empirically valid expectation for the rate of transmission events in cell  $M^{TF^P}$  in table 1. Therefore, the latter group provides the baseline comparison for the two groups in table 1 with vaccination-discordant regimens,  $M^{TF^P}$  and  $M^{PF^T}$ , whereas the concordant group with both partners receiving Gardasil ( $M^{TF^T}$ ) serves as a secondary control group where minimal transmission is expected to occur.

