We used the Bernstein and Lagakos approach to derive sample size projections for different levels of power (80% and 90%), with type one error of 0.05, and one-sided hypothesis for reductions in the above rate of transmission varying between 30% and 70%, i.e., the expected magnitude of the protective effect in the discordant vaccination groups where the partner receiving placebo is the one to be protected. We also assumed gender equivalent rates of transmission as per our findings in the HITCH study. At 80% power we would require 97 couples per group (cells in table 1) to detect a significant 40% reduction in transmission of vaccine-targeted types. A group size of 80 couples per group would be required to attain 90% power to detect a 50% reduction. The latter can be statistically detected with as little as 59 couples per group if we relax power to 80%. Evidently, larger effect sizes will have reduced requirements. There are no published empirical estimates of the expected level of transmission reduction, but our informal consultation with experts in the field, including [name], a member of our Steering Committee (see below), indicates that 40%-50% reduction in transmission is a conservative estimate for the protective effect to a partner of a vaccinated individual.

HITCH, the closest recruitment platform that TRAP-HPV will be based on, has a cumulative 16% loss to follow-up at month 12, which translates to a per-visit attrition rate of 2.7%. By applying the same expectation of losses to follow-up and using the most stringent definition of projected sample size (at 90% power and 40% effect size), we therefore propose to enroll 125 couples per group for a total of 500 couples. It is noteworthy that vaccine efficacy against HPV infection can occur with only two and even one dose. As we have observed in HITCH, the prevalence of vaccine-preventable types at enrolment is 23% and most transmission events occur early. Therefore, analyses of prevention of transmission events will begin to be informative from the second (2 months) visit and beyond.

**2.12 What is the planned recruitment rate? How will the recruitment be organized? Over what time period will recruitment take place? What evidence is there that the planned recruitment rate is achievable?**

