## **2.16 What is the proposed type of analyses?**

### *Statistical Analysis*

We hypothesize that HPV vaccination is effective in reducing the risk of HPV transmission to their sexual partners. The above plan takes advantage of the opportunity for measuring transmission events in multiple mucosal sites for multiple HPV types, over multiple clinic visits, and in both directions (i.e., male-to-female and female-to-male). We will take advantage of advanced regression methods as framework for measuring the effects expected via HPV vaccination.

In the simplest core formulation (e.g. analyzing a single HPV type and a single mucosal site), we will use the Kaplan-Meier technique to plot the cumulative probability of HPV infection in sexual partners of vaccinated versus unvaccinated individuals against follow-up time. Using the layout in table 1, this implies comparing the HPV infection histories of women in the  $M^T F^P$  and  $M^P F^P$  groups and of men in the  $M^P F^T$  and  $M^T F^P$  groups. Expectedly, protection is also likely to occur via cumulative effects observable via HPV DNA detection in multiple mucosal sites. Similar time-to-event analyses will be conducted to examine these pan-mucosal site effects.

Statistical comparisons in the HPV transmission between vaccine and control groups will be determined using the log-rank test. The Cox proportional hazard regression model will be used to estimate the effect of vaccination on transmission of HPV to sexual partners. Time to HPV infection will be defined in days as the time from study enrolment to the date of infection. Hazard ratios (HR) and their respective 95% confidence intervals will be computed. Statistical analyses will follow an intention-to-treat approach but additional regression models will examine the role of several candidate determinants in mediating transmission and the protective effects.

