**Close recruitment early**

Recruitment in the TRAP-HPV study has been a challenge, and more so since the start of the COVID-19 pandemic. We had to cease study-related activities (mostly occur among student populations) from March 13 to June 2020 under the COVID-19 lockdown measures announced by the Quebec Government and by extension the McGill Research and Graduate Studies Offices at the Faculty of Medicine and Health Sciences. We resumed research activities on July 28, 2020, but most student populations continued online learning. Study recruitment continued to be a challenge; only 19 new couples were recruited over the last two years.

In order to maintain the scientific value of the TRAP-HPV study as well as allocate the remaining study funds to test the collected biological samples and pay the remuneration for all pending study visits, we are:

- 1- Closing recruitment as we will never be able to reach the target sample within a reasonable timeframe. The last couple was recruited on February 16, 2022.
- 2- Completing the follow-up of existing couples. However, we are proposing to eliminate Visit 6 and stop follow-up at Visit 5 (one assessment point post-vaccination with the third dose of the vaccine). By design, six study visits are scheduled over a one-year period (at enrollment [month 0], and at 2, 4, 6, 9, and 12 months) and the vaccines are administered at three visits (0, 2, and 6 months). We anticipate by this to complete the study by

November 2022 (rather than February 2023 if we were to keep Visit 6). However, because of the usual delays for students to adhere with the expected date of appointments keeping Visit 6 will actually impose an inordinately long study duration.

For couples who will not have a visit 6, compensation will be modified to \$100/person (\$200/couple) instead of \$80/person (\$160/couple) for Visit 5.

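### Section 2.11 still states 90% power from 500 couples, but recruitment closed at 188 and no power, detectable effect or precision is given for that number

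*Combined protocol and SAP*

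**What the plan says.** Section 2.11 takes its control rate from the sponsor's earlier couples cohort: "The rate of acquisition of any of these types was 3.8 per 100 subject-months", which it equates to roughly 40% cumulative incidence. The test has a type I error of 0.05 and a "one-sided hypothesis for reductions in the above rate of transmission varying between 30% and 70"%. Three sizes per cell are printed: 97 (80% power, 40% reduction), 80 (90% power, 50% reduction) and 59 (80% power, 50% reduction). Of the last it says "The latter can be statistically detected with as little as 59 couples per group if we relax power to 80"%. For 90% power and a 40% reduction, with 16% loss at month 12, it concludes "we therefore propose to enroll 125 couples per group for a total of 500 couples".

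The amendment history records "Close study recruitment at 188 couples instead of the original 500 couples". Appendix 1 (closing recruitment early) gives the reason, "Closing recruitment as we will never be able to reach the target sample within a reasonable timeframe", and adds for couples still in follow-up that "we are proposing to eliminate Visit 6 and stop follow-up at Visit 5". Neither place restates power, detectable effect or precision. The Gardasil 9 entry in Appendix 1 argues that nine types lower the required size, but gives no revised number and predates the closure.

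Section 2.16 plans Kaplan-Meier curves, a log-rank test and Cox regression: "The Cox proportional hazard regression model will be used to estimate the effect of vaccination on transmission of HPV to sexual partners".

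**The concern.** The only quantitative statement of what the trial can detect belongs to a trial 2.7 times larger (500/188). A reader of section 2.11 would take a non-significant result as evidence from a study with 90% power. The results are meant to feed models of vaccinating boys (sections 1.1 and 1.5), so reading an imprecise null as no transmission effect would matter.

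The 90%/500 statement cannot simply be scaled down. Its working is not shown, 125 does not agree with the 97 beside it, and the answer for 188 depends on a contrast and type set that the protocol describes in different ways.

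**Working it through.** **Inputs.** Control rate 0.038 per month, 12 months, one-sided 0.05, reductions of 40% and 50%, 16% loss (section 2.11); 188 couples (amendment history). Assumed: equal cells, 188/4 = 47. Comparator: M^P F^P for both sexes, as in section 2.8. z-values: 1.645 (alpha), 0.842 (80%), 1.282 (90%).

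**1. The printed sizes.** Two-proportion formula: n = [1.645√(2p̄(1−p̄)) + z_β√(p1(1−p1) + p2(1−p2))]² / (p1−p2)².
- Control 40%: 105, 89 and 64, against 97, 80 and 59.
- Control 42%: 97, 82 and 60, within 2 couples. On this reading the sizes are before loss.
- A rate-ratio calculation pooled over sexes and divided by 0.84 gives 97.4, 81.0 and 58.5. On this reading they are already net of loss.

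Both readings fit, and the protocol does not say which was used.

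**2. The 125.** Going from 80% to 90% power multiplies n by (1.645 + 1.282)²/(1.645 + 0.842)² = 1.385. So 97 × 1.385 = 134, and 134/0.84 = 160 if 97 is before loss. Neither is 125. (105/0.84 = 125 matches the 80% power size at 40% control, but the protocol does not say it was obtained that way.)

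**3. Scaling the printed sizes to 47.**
- 40% reduction: Φ(2.487√(47/97) − 1.645) = Φ(0.086) = 53%.
- 50% reduction: Φ(2.487√(47/59) − 1.645) = Φ(0.575) = 72%.

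**4. Log-rank scale, by sex, no loss.** Events per cell = 47(1 − exp(−0.456·HR)): 17.2 (control), 11.3 (HR 0.6), 9.6 (HR 0.5).
- SE of log HR at 0.6 = √(1/17.2 + 1/11.3) = 0.383.
- Expected 95% CI = 0.6·exp(±1.96 × 0.383) = 0.28 to 1.27.
- Power at HR 0.6: Wald Φ(0.511/0.383 − 1.645) = 38%; Schoenfeld Φ(0.511√28.5/2 − 1.645) = 39%.
- HR detectable at 80% power: 0.31 by Wald, 0.37 by Schoenfeld. A simulated log-rank test has 86% power at 0.31 and about 80% at 0.35, so 0.35 is the usable figure.

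**5. Pooled over both directions** (94 v 94 persons, partners independent). SE = 0.383/√2 = 0.271, so the CI is 0.35 to 1.02.

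| No loss, four types | Power, 40% reduction | Power, 50% reduction | Detectable HR, 80% power | 95% CI at HR 0.6 |
|---|---|---|---|---|
| Log-rank, by sex | about 38% | about 54% | about 0.35 | 0.28–1.27 |
| Log-rank, pooled | about 60% | 78%–81% | about 0.5 | 0.35–1.02 |
| Two proportions (control 40%–42%), by sex | 51%–53% | 69%–71% | – | – |
| Two proportions (control 40%–42%), pooled | 76%–79% | 92%–93% | – | – |

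M^P F^P couples contribute both partners. At an assumed partner correlation of 0.33–0.49, pooled log-rank power for a 40% reduction falls to 54%–51%.

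**6. With 16% loss** treated as exponential censoring, c = −ln(0.84)/12 = 0.0145 per month. Events per cell = 47·λ/(λ+c)·(1 − exp(−12(λ+c))) = 15.9 and 10.4 at HR 0.6. By-sex power is 36%–37% (40% reduction) and 50%–53% (50% reduction), CI 0.27–1.31. Pooled power is 57%–58% and 76%–79%, CI 0.35–1.04. On the two-proportion scale at 40% control, removing lost couples gives 45% and 61% by sex (39 per cell), and 70% and 87% pooled (79 v 79).

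**7. Visit 6.** If 19 couples (assumed: those recruited in the last two years) stop at month 9, power falls by less than 1 point. If all couples did, an extreme bound, it would fall by 6–9 points.

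**8. What the figure would refer to.**
- Section 2.8: four types; placebo partners in both discordant cells against M^P F^P; type concordance is also called the main outcome.
- Section 2.11: any of four types; M^T F^P is printed as the baseline, although it is also one of the discordant cells.
- Section 2.16: contrasts written by sex for the simplest formulation; the men's comparator is printed as M^T F^P.
- Appendix 1, Gardasil 9: nine types, with power said to rest on individual types and not the combined group.

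**The case against.** The shortfall is not hidden: Appendix 1 says openly that the target is out of reach. An amendment entry that differs from older text is not in itself an error. Section 2.16 already promises hazard ratios with 95% CIs, so imprecision will show. Section 2.17 describes the study as estimation, not a basis for regulatory approval. With recruitment closed, a new power figure changes no decision. This is a good reason to lead with expected CI width instead of power. It does not supply that width, and section 2.11 still carries the superseded claim.

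Nine types might be thought to restore power. Scaling by the dyad prevalences (61.22/35.36 = 1.73) gives an assumed any-of-nine incidence of 55%–69%. Log-rank power in one direction is then about 50%–60% for a 40% reduction before loss; on the two-proportion scale at 69% it is 86%. No any-of-nine endpoint is named, however, and the Gardasil 9 entry points to individual types.

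Three stronger readings are tempting and are not supported:
- That the contrast and type set are missing. They are named in sections 2.8, 2.11 and 2.16; the fault is inconsistency and lack of update.
- That the trial will miss a true 40% reduction about three times in five. That holds for a by-sex log-rank test at the 3.8 rate. The two-proportion reading, which fits the printed sizes about as well, gives roughly one in two.
- That the trial can show little. Pooled, with independent partners and a 50% reduction, power is about 80% on the log-rank scale.

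**Conclusion.** The point stands as an omission plus an arithmetic inconsistency. The stated 90% power for 500 couples no longer applies, 188 couples fall below every printed size, and nothing replaces the statement. The 125 was already short of the 134 (or 160) implied by the section's own 97.

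Confidence is high for the omission and moderate for any single power figure. By sex, with four types and before loss, power for a 40% reduction lies between about 38% and 53% depending on scale; pooled with independent partners, between about 60% and 79%. By sex, none of these four-type calculations reaches 80% for a 40% or 50% reduction, the range that section 2.11 calls conservative.

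The figures assume equal cells, one any-of-four event per person and the earlier cohort's rate. They ignore interim alpha spending (section 2.17), prior HPV vaccination (Appendix 1) and the multi-type, multi-site models of section 2.16, so they are illustrative.

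**What to change.** 1. Withdraw the 90%/500 statement as a description of the trial as conducted, and show how 97, 80, 59 and 125 were obtained or mark them as superseded.
2. Before analysis, name one contrast (by sex, or both discordant cells pooled against M^P F^P) and one type set (four or nine; any-type or type-specific). Reconcile sections 2.8, 2.11, 2.16 and Appendix 1 with that choice, including the comparator cell printed for men.
3. For 188 couples and actual cell counts, state the expected 95% CI and the effect detectable at 80% power on the scale of the planned analysis, with working, with and without 16% loss, and with the follow-up window stated. Give no nine-type figure unless a nine-type endpoint is named.
4. Add a sentence that a non-significant result will not be read as absence of effect.
5. If a pooled contrast is chosen, stratify the Cox model by sex, cluster the variance on couple, and report sex-specific HRs with 95% CIs beside it. Ignoring the clustering gave a simulated type I error of 0.056–0.067 at partner correlations of 0.33–0.49.

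The cost is SAP wording; no new data are needed. Whether to pool is the sponsor's choice and has a price: the plan assumes equal transmission rates by sex, not equal vaccine effects. If the reduction were 40% in one direction and 20% in the other, pooled log-rank power would be about 39%–40%, no real gain over 38% for the stronger direction alone.

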**2.13 Are there likely to be any problems with compliance? On what evidence are the compliance figures based?**

Although TRAP-HPV is complex in design and number of procedures, we are confident that there will be high compliance because of our inclusion and exclusion criteria, which will select only highly motivated couples (see section 2.5). Management will be done by a team that is highly experienced in conducting studies of HPV infection in couples. Participants will be administered the intervention at the clinic and attend follow-up visits much like the ones in our previous studies, such as the most recent HITCH study, which was successful in terms of retention and in maintaining constant contact with the couples. In any case, our sample size calculations took the anticipated losses into consideration.

**2.14 What is the likely rate of loss to follow up? On what evidence is the loss to follow-up rate based?**

Data from our HITCH couples' cohort, which has just completed accrual of 502 couples and is approaching completion of all follow-up visits, indicates an average per-visit loss to follow-up of 2.7% for a cumulative 16% attrition after 6 visits in one year. TRAP-HPV will be based on the same source population and will use the same team and comparable methodology and we have incorporated these estimates into our sample size calculation. Since we plan to offer participants a

generous incentive to remain in the study, the rate of loss to follow-up is expected to be just as low as it was in HITCH or even lower (we did not screen couples for their stability in HITCH).

## **2.15 How many centres will be involved?**

The Student Health Services of McGill and Concordia Universities in Montreal will serve as recruitment centres. Study oversight and data management will be carried out at McGill's Division of Cancer Epidemiology (MDCE), directed by the PI. This unit has all the resources necessary to carry out large molecular epidemiological investigations. The MDCE is the central hub for a network of research activities related to the epidemiology and prevention of HPV infection and its associated diseases that involves epidemiologists, lab scientists, and clinicians in Montreal, in other Canadian provinces, and internationally.

## **2.16 What is the proposed type of analyses?**

### *Statistical Analysis*

We hypothesize that HPV vaccination is effective in reducing the risk of HPV transmission to their sexual partners. The above plan takes advantage of the opportunity for measuring transmission events in multiple mucosal sites for multiple HPV types, over multiple clinic visits, and in both directions (i.e., male-to-female and female-to-male). We will take advantage of advanced regression methods as framework for measuring the effects expected via HPV vaccination.

In the simplest core formulation (e.g. analyzing a single HPV type and a single mucosal site), we will use the Kaplan-Meier technique to plot the cumulative probability of HPV infection in sexual partners of vaccinated versus unvaccinated individuals against follow-up time. Using the layout in table 1, this implies comparing the HPV infection histories of women in the  $M^T F^P$  and  $M^P F^P$  groups and of men in the  $M^P F^T$  and  $M^T F^P$  groups. Expectedly, protection is also likely to occur via cumulative effects observable via HPV DNA detection in multiple mucosal sites. Similar time-to-event analyses will be conducted to examine these pan-mucosal site effects.

Statistical comparisons in the HPV transmission between vaccine and control groups will be determined using the log-rank test. The Cox proportional hazard regression model will be used to estimate the effect of vaccination on transmission of HPV to sexual partners. Time to HPV infection will be defined in days as the time from study enrolment to the date of infection. Hazard ratios (HR) and their respective 95% confidence intervals will be computed. Statistical analyses will follow an intention-to-treat approach but additional regression models will examine the role of several candidate determinants in mediating transmission and the protective effects.

Cumulative risk models may be fitted with type-specific transmission as an outcome. GEE models can be used to incorporate data across multiple types of HPV, which is an alternative approach for incorporating repeated HPV prevalence data across HPV types and across visits involving the same woman). In a single Generalized Estimating Equations (GEE) logistic regression model, we can treat type-specific infection events for each of the four different HPV types as separate transmission endpoints and then estimate the exposure effect on selected HPVs as a group, as we have published recently. Mixed-effects models will also be adopted for incorporating repeated HPV transmission data across HPV types and across visits involving the same subject.

Although they will be screened as per the likelihood of their stability, if couples break-up and end their relationship before their last visit, they will be censored of the study while still contributing follow-up time and visits with informative specimens. As mentioned above, vaccination protection is expected to begin as early as the first dose, thus even with a subset of visits for a few couples, we can expect to analyze reductions in transmission before the full set of visits is completed.

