**Figure 1: Study design and schedule of procedures**

## 2.8 What are the proposed primary and secondary outcome measures?

The primary outcome will be the reduction of HPV DNA positivity for the target HPV vaccine types (i.e., HPVs 6, 11, 16, and 18) in multiple anatomic sites in Havrix-treated sexual partners of persons who received Gardasil. These are the combinations  $M^T F^P$  and  $M^P F^T$  in table 1. The main control group for unhindered HPV transmission will be group  $M^P F^P$  and the full protection control group is represented by the combination  $M^T F^T$ .

We will measure prevalence and incidence of HPV 6, 11, 16, and 18 infections (via DNA detection by the PCR protocol described below) in all three samples (vaginal, anal, and oral, for women, and penile, anal, and oral, for men) for the above time points among all subjects. Specimens for all three sites will be collected during all six clinic visits.

We will not exclude subjects if they are positive for HPV DNA of HPVs 6, 11, 16, and 18 because we intend to verify whether protection conferred by vaccination (both self and partner's) extends to mucosal sites that have not yet been infected by the above target types. Actually, prevalent infections at enrolment will be informative because they could be the source of a transmission event to a partner.

Reduction in HPV type concordance (for the four target types) will be the main outcome evaluable as per the above group contrasts. These comparisons will be done with due attention to the enrolment virological status of the individuals. For instance, we expect that a Havrix-treated woman who is positive for HPV 6 in the anal specimen but negative for this type in the vaginal specimen may derive benefit if her partner receives Gardasil, even if he is HPV-6 positive in the penile sample. Our assumption is that protection via vaccination is pan-mucosal, via transudation of neutralizing antibodies; this protection may mediate transmission.

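### Section 2.16 compares placebo men who have a vaccinated partner with men who were vaccinated themselves, so the female-to-male contrast does not estimate partner protection and can point the wrong way

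*Combined protocol and SAP*

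**What the plan says.** Table 1 defines four cells by the man's and the woman's vaccine (T = HPV vaccine, P = hepatitis A control vaccine).

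- **Section 2.8** defines the primary outcome "in Havrix-treated sexual partners of persons who received Gardasil" and assigns the control roles: "The main control group for unhindered HPV transmission will be group $M^P F^P$ and the full protection control group" is M^T F^T.
- **Section 2.16** gives the purpose of the Kaplan-Meier comparison as the "cumulative probability of HPV infection in sexual partners of vaccinated versus unvaccinated individuals". For women this means "comparing the HPV infection histories of women in the $M^T F^P$ and $M^P F^P$ groups". For men it means the histories "of men in the $M^P F^T$ and $M^T F^P$ groups".
- **Section 2.11** takes the acquisition rate seen in unvaccinated HITCH participants and says that it "is the most empirically valid expectation for the rate of transmission events in cell $M^{TF^P}$ in table 1". The next sentence uses that cell as the baseline for the two discordant cells, and M^T F^P is one of those two.

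No other section states a men's contrast for the Kaplan-Meier, log-rank or Cox analyses. The GEE and mixed models in section 2.16 name no cells.

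**The concern.** The women's contrast holds the woman's own vaccine fixed at placebo and varies only her partner's. That is what an effect on transmission to the partner requires. The men's contrast does not do this: M^P F^T men had placebo and a vaccinated partner, while M^T F^P men had the HPV vaccine and a placebo partner. Own and partner vaccination change together, in opposite directions, and no analysis of those two cells alone can separate them.

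The result sets indirect protection against direct protection. If the vaccine protects the recipient more than it protects the partner, a real benefit to male partners would appear as an excess of infections. Female-to-male transmission is one of the two directions that the trial set out to measure. With recruitment closed at 188 couples instead of 500, there is little information to spare in either direction.

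**Working it through.** **Inputs from the documents**
- Acquisition rate 3.8 per 100 subject-months, stated as about 40% cumulative incidence (section 2.11). Check: 1 − exp(−0.038 × 12) = 36.6%, close to the stated figure. I use 40%.
- Expected partner effect 40%–50% (section 2.11).
- Planned size 125 couples per cell with 16% loss (section 2.11): 125 × 0.84 = 105 evaluable. Actual enrolment 188 couples: 188/4 = 47 per cell if the cells are equal (assumption).
- One-sided type I error 0.05 (section 2.11).

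**Assumption.** The documents call the vaccine highly effective and say that it is efficacious in men, but they give no direct-efficacy figure for this endpoint. I vary it from 0% to 95%.

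**Formulas.** Let b be the baseline risk, s the partner effect and d the direct effect.
- Intended contrast, M^P F^T vs M^P F^P: b(1 − s)/b = 1 − s.
- Contrast as written, M^P F^T vs M^T F^P: b(1 − s)/[b(1 − d)] = (1 − s)/(1 − d).

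The baseline cancels, so the distortion does not depend on the 40% figure.

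**Risk ratios.** With s = 40%, M^P F^T men have risk 0.40 × 0.60 = 0.24 and the correct ratio is 0.60. With s = 50% the correct ratio is 0.50, and with no partner effect it is 1.00. As written:

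| Direct effect d (assumed) | Risk in M^T F^P men | s = 40% | s = 50% | s = 0 |
|---|---|---|---|---|
| 0% | 0.40 | 0.60 | 0.50 | 1.0 |
| 30% | 0.28 | 0.86 | 0.71 | 1.4 |
| 40% | 0.24 | 1.00 | 0.83 | 1.7 |
| 50% | 0.20 | 1.20 | 1.00 | 2.0 |
| 70% | 0.12 | 2.00 | 1.67 | 3.3 |
| 90% | 0.04 | 6.00 | 5.00 | 10 |
| 95% | 0.02 | 12.0 | 10.0 | 20 |

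The ratio is right only at d = 0. It passes 1 when d exceeds s.

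**Chance of each conclusion** (two-proportion test, one-sided 0.05, b = 40%, s = 40%):

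| | 105 per cell | 47 per cell |
|---|---|---|
| Correct contrast shows benefit | 80% | 51% |
| As written shows benefit, d = 30% | 16% | 11% |
| As written shows benefit, d = 50% | 1% | 2% |
| As written significant in the wrong direction, d = 50% | 17% | 12% |
| As written significant in the wrong direction, d = 70% | 73% | 45% |
| As written significant in the wrong direction, d = 90% | 99.6% | 88.5% |

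**The plan's sample sizes.** Section 2.11 gives 97, 80 and 59 couples per cell. The two-proportion formula with the stated inputs gives 105, 89 and 64. A baseline near 42% would come close (97, 82, 60), as would accrual assumptions that the plan does not state. This point does not rest on those figures.

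**The case against.** The strongest reply is that this is a mislabelled cell, not a chosen analysis. The women's contrast in the same sentence, the definition in section 2.8 and the statement in section 2.11 that the placebo partner is the one to be protected all point to M^P F^P. The slip in section 2.11 changes no number, because the rate used there is the unvaccinated rate whatever the cell is called. The point also turns on a superscript in text extracted from a PDF, so the original page should be checked.

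Most of this is fair, and a slip is the likeliest explanation. It does not remove the problem. The section 2.16 labels read cleanly in current text, no other section gives a correct men's contrast, and an analyst who follows the plan literally would run the wrong comparison. M^T F^P men do have unvaccinated partners, so the contrast meets the stated purpose on partner status, but with own vaccination fully confounded.

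Two qualifications stand. First, reversal is conditional. Participants who are DNA-positive at entry are kept, time runs from enrolment, most transmission is early, and Appendix 1 allows people with earlier HPV vaccination to enter. Each could dilute the direct effect, and at 30% the answer is biased (0.86) but not reversed. The ratios of 12 and 20 are extremes. Second, the contrast is written for the simplest formulation, a single type and site. The log-rank and Cox text does not restate the cells, and the GEE and mixed models are not tied to them.

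**Conclusion.** The concern holds. As written, the men's contrast in section 2.16 does not estimate protection of male partners and contradicts the primary outcome and control group in section 2.8. With a true ratio of 0.60, it would give 0.86 at 30% direct efficacy, 1.20 at 50% and 6.00 at 90%. The sign reverses if the direct effect exceeds the partner effect. That is plausible for a vaccine that the plan calls highly effective, but the documents give no figure that settles it. These ratios assume that each discordant cell carries one effect only and that the man's unprotected risk is the same in every cell. Only the female-to-male direction is affected; the women's contrast is correct. The mislabelled baseline cell in section 2.11 has no numerical effect but should be put right with it.

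**What to change.** 1. In section 2.16, change the men's comparison to M^P F^T versus M^P F^P, and say that the log-rank and Cox analyses use the same cells.
2. In section 2.11, relabel the baseline cell M^P F^P.
3. Keep M^T F^P versus M^P F^P in men for the separate question of protection of the recipient (section 2.18).
4. Check the labels against the original page before issuing the correction.

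These are wording changes. All four cells are already in the design, so they need no new data and place no burden on participants. The documents expected follow-up to end by November 2022 and do not say whether analysis has begun. If it has, confirm which male cells were compared, rerun the contrast if needed, and record the correction with its date and whether outcome data had been seen.
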